## 7.3 Endpoints

**7.3.1 The primary efficacy analysis** will be the log transformed change in intrasubject plasma VEGF-D before and 1 month after initiation of monotherapy imatinib mesylate. Log transformation was needed in the MILES study because this serum concentration can often go quite high in some patients. VEGF-D will be obtained at baseline and at 28 and 56 days after initiation of imatinib. Note that this analysis will allow the use of sirolimus using and sirolimus naïve participants.

**7.3.2 Secondary endpoints** are obtained to test both efficacy and inform about quality of life. Quality of life questionnaire instruments are described in a later attachment as guided by the CDMRP program. Importantly, respiratory specific and general quality of life scores will be used in the study. Recently, the St Georges Respiratory Questionnaire (SGRQ) was retrospectively validated against four anchors in the MILES study and will be used as a secondary efficacy endpoint in the combined analysis of both stratified randomization populations. To minimize multiplicative analysis, 3 endpoints are chosen for combined population secondary endpoints: Intrasubject Change in FEV1 (ml), Intrasubject Change in FVC (ml), and Intrasubject Change in SGRQ (points) between the timepoints of Baseline and 1 month after initiation of monotherapy imatinib/placebo. The last secondary endpoint compares a 2 month treatment with imatinib/placebo in sirolimus naive participants on intrasubject change in log VEGF-D (pg/ml).

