## 6. ETHICAL CONSIDERATIONS

This study will be initiated only after a thorough review by the MUSC IRB, the Columbia University IRB, and the Human Research Protection Office (HRPO) of the US Army Military Department. A written informed consent will be obtained from every participant in which known side effects of imatinib are described. Participants may participate in this study and request that their biosamples be anonymized and/or not stored after the study analysis is complete.

An important consideration for this study is that sirolimus is not currently FDA approved for LAM. However, it is estimated that 90% of individuals with LAM and low lung function are using this drug and efforts are underway by [name], principal investigator of the MILES trial and medical director of the LAM Foundation to obtain FDA approval via his IND for sirolimus. This study is submitted because no study in LAM will advance in this rare disease population unless individuals on sirolimus are allowed to be enrolled since the disease is so rare. A study approved by the CDMRP in 2010 (the TRAIL trial) failed to achieve adequate enrollment because of this issue. Importantly, individuals enrolled in this study are on unchanging doses of sirolimus.

Subjects will be instructed at the beginning of the study to report to the investigator any adverse physical or mental changes they experience and they will be asked about adverse events at each visit, including those experienced at the baseline visit prior to, during, or immediately following treatment. All such adverse events reported by the subjects or observed by the investigators will be captured in the study forms. If the event is deemed to be Serious, the serious adverse events procedures will be followed and the IRB, DSMB, HRPO and Novartis notified.

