## 7. STATISTICAL ANALYSIS

## 7.1 Sample Size

Since this is a pilot study, the estimate of sample size to determine a biologic signal in patients with LAM is extrapolated from other studies in which serial samples of VEGF-D has been measured. Since LAM is a rare disease a small trial is designed to assure enrollment is achievable. This study will enable proper powering of subsequent studies. The authors believe that a proof of principal pilot study will be able to recruit 20 participants, the majority on rapamycin, for this study. A larger study is not possible given the limitations of funding.

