## 7.2 Statistics

Statistical analysis of the primary endpoint will compare the VEGF-D before and one month after imatinib montherapy by intrasubject testing. VEGF-D has been shown to be logarithmically expressed and log transformation of the data is planned. It is unlikely that data will be normal between the imatinib and placebo groups. Therefore, the intrasubject difference (log pg/ml) in VEGF-D between imatinib and placebo groups will be subjected to non-parametric analysis with Wilcoxen rank sum tests. All statistical tests will be 2-sided at a 0.05 level of significance.

Statistical analysis of secondary endpoints will be performed in identical manner using the % change in FEV1 and FVC for these analyses. Use of ml change disproportionately shows effects in this bronchodilator responsive disease for those with preserved lung function. All secondary endpoints will be reported in study manuscripts with adjustment for multiplicity testing. Data will be presented in spaghetti plots to allow an assessment for responder analysis.

Exploratory analyses are designed to not miss a biologic signal if present. The impact of any significant difference between groups will require additional study and will be presented as question generating and will not use adjustments for multiplicity testing.

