## 7.3.3 Exploratory endpoints

The table below lists the exploratory endpoints that will be collected to define if there is a difference between the 4 populations in the study. All change variables are measured intrasubject.

Efficacy Endpoints	Difference in baseline and 1 month after initiation of monotherapy imatinib/placebo	Difference in baseline and 1 month in patients on sirolimus	Difference in baseline and 2 months in imatinb naive participants
Change in VEGF-D (log pg/ml)	X (Primary)	X (Exploratory)	X (Secondary)
Change in FVC (%)	X (Secondary)	X (Exploratory)	X (Exploratory)
Change in FEV1 (%)	X (Secondary)	X (Exploratory)	X (Exploratory)
Change in mMRC Dyspnea (score)	X (Exploratory)	X (Exploratory)	X (Exploratory)
Change in 6MWT distance (M)	X (Exploratory)	X (Exploratory)	X (Exploratory)
EQ-5D (score)	X (Exploratory)	X (Exploratory)	X (Exploratory)
Functional Assessment	X (Exploratory)	X (Exploratory)	X (Exploratory)

Inventory (score)			
SGRQ (score)	X (Secondary)	X (Exploratory)	X (Exploratory)

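### The fourth secondary endpoint is a formal test in sirolimus-naive participants only, a group probably too small to reach significance, yet it sits in the multiplicity-adjusted family

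*Combined protocol and SAP*

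**What the plan says.** Section 7.3.2 names four secondary endpoints. Three (FEV1, FVC and SGRQ) use all participants: "3 endpoints are chosen for combined population secondary endpoints". The fourth is restricted: "The last secondary endpoint compares a 2 month treatment with imatinib/placebo in sirolimus naive participants on intrasubject change in log VEGF-D (pg/ml".

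For the test, section 7.2 says that the primary endpoint "will be subjected to non-parametric analysis with Wilcoxen rank sum tests", two-sided at 0.05, and then: "Statistical analysis of secondary endpoints will be performed in identical manner". On multiplicity it says: "All secondary endpoints will be reported in study manuscripts with adjustment for multiplicity testing". It names no adjustment method.

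On how many participants will be off sirolimus, section 7.1 expects that the trial "will be able to recruit 20 participants, the majority on rapamycin, for this study". Section 5.1 describes those off the drug as few. Section 6 says that "it is estimated that 90% of individuals with LAM and low lung function are using this drug". No visible text gives a planned or minimum size for the naive group, or a rule for reporting it descriptively if it is too small.

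The population is labelled in three ways. Section 7.3.2 says sirolimus naive. The 7.3.3 table heads the column "Difference in baseline and 2 months in imatinb naive participants". Section 5.4 stratifies randomization on sirolimus use in the last month, which is not the same as never having used it.

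**The concern.** A rank-sum test on very few participants has a floor. However cleanly the arms separate, the exact p cannot fall below a value set by the group sizes alone. If the naive group is as small as the documents suggest, that floor lies above 0.05 and the result is fixed before any data are collected.

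Two things are at stake. First, this is the only primary or secondary VEGF-D comparison confined to participants who have no sirolimus withdrawal during the trial. A non-significant result that was unavoidable could be misread as evidence against imatinib monotherapy, in a pilot meant to inform a phase 3 design. Second, a fourth test in the adjusted family makes the other three harder to pass under the common adjustment methods.

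**Working it through.** The plan has no calculation to reproduce. Section 7.1 rests the 20 participants on feasibility and funding, with no power, effect size or standard deviation.

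**Inputs from the documents**
- Total 20 (7.1), with 10 imatinib and 10 placebo sets prepared (section 6), so equal allocation.
- A majority on rapamycin (7.1): at least 11 on, so at most 9 off.
- 90% sirolimus use among patients with low lung function (section 6): 10% not using it.
- Two-sided 0.05, rank-sum test (7.2).
- Four secondary tests: three combined-population and one naive-only (7.3.2).

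**Assumptions**
- Non-use rates of 20% and 30%, as sensitivity values.
- Bonferroni, Holm or Hochberg as the adjustment.
- An exact rank-sum p, which is appropriate at these sizes.

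**Step 1. Expected naive count at the 90% figure.** 20 × (1 − 0.90) = 2, that is 1 against 1.

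**Step 2. Smallest possible exact two-sided p.** With n naive participants, k of them in one arm, complete separation gives p = 2 / C(n, k), capped at 1. The most even split gives the lowest value.

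| n | split | 2 / C(n, k) | smallest p |
|---|---|---|---|
| 2 | 1 v 1 | 2/2 | 1.000 |
| 4 | 2 v 2 | 2/6 | 0.333 |
| 6 | 3 v 3 | 2/20 | 0.100 |
| 7 | 3 v 4 | 2/35 | 0.057 |
| 8 | 4 v 4 | 2/70 | 0.029 |
| 9 | 4 v 5 | 2/126 | 0.016 |
| 10 | 5 v 5 | 2/252 | 0.008 |

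So 8 naive participants are needed before 0.05 is attainable even without adjustment.

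**Step 3. Chance of at least 8.** With X ~ Binomial(20, q), P(X ≥ 8) = Σ C(20, x) q^x (1 − q)^(20 − x) over x = 8 to 20.
- q = 0.10: 0.0004
- q = 0.20: 0.032
- q = 0.30: 0.228

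At q = 0.10, P(X ≥ 2) = 0.608, so the chance of fewer than 2, and hence no comparison between arms at all, is 1 − 0.608 = 39%.

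**Step 4. Effect of the adjustment on this test.** Bonferroni over four tests gives 0.05/4 = 0.0125. With 9 naive participants the floor is 2/126 = 0.0159, above 0.0125, so Bonferroni is out of reach for any count consistent with a majority on rapamycin. The Holm steps are 0.0125, 0.0167, 0.025 and 0.05. With 9, the floor of 0.0159 can pass the second step if another endpoint is rejected first. With 8, 0.0286 can pass only the last step, after all three others. Under Hochberg, 8 can succeed only if all four p values are at or below 0.05. In each of these cases other endpoints must succeed too.

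**Step 5. Cost to FEV1, FVC and SGRQ.** Under Bonferroni their level is 0.05/4 = 0.0125 with the naive test in the family and 0.05/3 = 0.0167 without it. If the naive test cannot be rejected, the Holm and Hochberg thresholds for the other three are 0.0125, 0.0167 and 0.025 instead of 0.0167, 0.025 and 0.05. For scale, take 10 per arm, an assumed effect of 1.25 SD and the normal approximation, power = Φ(1.25 × √(10/2) − z). This gives Φ(2.795 − 2.498) = 61.7% at 0.0125 and Φ(2.795 − 2.394) = 65.6% at 0.0167, a difference of about 4 percentage points.

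**The case against.** The strongest reply is that the size of the naive group is not known. A reader might infer that exactly 2 of 20 will qualify. The documents do not say so: the 90% describes patients with low lung function in general, while section 5.3.1 admits anyone with FVC or post-bronchodilator FEV1 below 90% predicted. Section 5.1 speaks of enrolling on- and off-sirolimus participants differentially, and the study-schedule figure is not shown and might carry stratum numbers. This stands, so the conclusion is given across a range of rates. In the other direction, strictly naive participants may be fewer than those off sirolimus in the last month.

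A reader might also infer that the cost to the other endpoints is certain. It is not, because no method is named. As the last step of a fixed sequence, this test would cost them nothing.

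The plan does not specify an exact p. The normal approximation without continuity correction can fall to 0.0495 with 6 participants, but it is unreliable at that size. With the correction it is 0.0518 at 7.

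Nor does the monotherapy aim rest on this subgroup. The primary VEGF-D endpoint uses both strata, and the 7.3.3 table lists seven other variables for the same 2-month comparison. Section 4.6 already warns that differences in lung function and quality of life are unlikely to reach significance, and section 7.2 already plans spaghetti plots. These points limit the damage. They do not give the test a realistic chance of success.

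**Conclusion.** The point holds as a matter of probability. With 7 or fewer sirolimus-naive participants, exact significance at 0.05 is impossible whatever imatinib does. The chance of 8 or more is 0.0004 if non-use is 10%, 3% at 20% and 23% at 30%; the last two rates are assumptions. If the adjustment is Bonferroni over four tests, even 9 is not enough. Under Holm or Hochberg, 8 or 9 could succeed only alongside other endpoints. The test therefore very probably cannot succeed, and it costs the other three endpoints a modest amount under any of those three methods.

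The documents do not support calling a null result guaranteed, since the stratum size and the adjustment method are both open. Nor do they support reading the 7.3.3 heading as a plan to pool all 20 participants. Section 7.3.2 names the sirolimus-naive population, so the heading is more likely a drafting slip, but the two texts disagree and need reconciling.

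**What to change.** In section 7.3.2 and the 7.3.3 table, move the sirolimus-naive 2-month log VEGF-D comparison to descriptive or exploratory reporting: individual trajectories and median change by arm, outside the adjusted family. Leave FEV1, FVC and SGRQ as the adjusted secondary endpoints, and name the adjustment method. State that a null result in this subgroup is not evidence that monotherapy has no effect.

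Reconcile the population label across sections 7.3.2, 7.3.3 and 5.4. Never having used sirolimus and not having used it in the last month are different populations, so the choice should be explicit.

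If the sponsor prefers to keep a formal test, placing it last in a fixed sequence with a stated minimum group size would remove the cost to the other endpoints, but not the floor on p.

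The change is wording only, with no loss of data or visits. The sponsor gives up a formal secondary claim on this subgroup that the trial is unlikely to be able to support.

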## 7.3.3 Exploratory endpoints

The table below lists the exploratory endpoints that will be collected to define if there is a difference between the 4 populations in the study. All change variables are measured intrasubject.

Efficacy Endpoints	Difference in baseline and 1 month after initiation of monotherapy imatinib/placebo	Difference in baseline and 1 month in patients on sirolimus	Difference in baseline and 2 months in imatinb naive participants
Change in VEGF-D (log pg/ml)	X (Primary)	X (Exploratory)	X (Secondary)
Change in FVC (%)	X (Secondary)	X (Exploratory)	X (Exploratory)
Change in FEV1 (%)	X (Secondary)	X (Exploratory)	X (Exploratory)
Change in mMRC Dyspnea (score)	X (Exploratory)	X (Exploratory)	X (Exploratory)
Change in 6MWT distance (M)	X (Exploratory)	X (Exploratory)	X (Exploratory)
EQ-5D (score)	X (Exploratory)	X (Exploratory)	X (Exploratory)
Functional Assessment	X (Exploratory)	X (Exploratory)	X (Exploratory)

Inventory (score)			
SGRQ (score)	X (Secondary)	X (Exploratory)	X (Exploratory)

## 7.4 Study Limitations

Study limitations include that the exact mechanism by which imatinib kills LAM cells remains unknown. The Bcr-Abl pathway has many downstream pathways including the Ras/MapK pathway, which leads to increased proliferation due to increased growth factor-independent cell growth. It also affects the Src/Pax/Fak/Rac pathway that affects the cytoskeleton leading to increased cell motility and decreased adhesion. The PI/PI3K/AKT/BCL-2 pathway is also affected altering mitochondrial stability. The JAK/STAT pathway, responsible for cellular proliferation is also affected by imatinib. While further laboratory studies on LAM/AML cells with alternative agents and mechanisms will continue, the current safety profile for imatinib use in humans is sufficient to begin a clinical trial in LAM prior to definitive mechanism of its effect on LAM cells is known.

The study is small and of short duration. The time interval for LAM cells *in vivo* to grow once removed from the influence of sirolimus is unknown. The study design in this rare disease is based on experience from LAM patients that remains anecdotal. However, in balancing safety and the potential to see a signal of efficacy in a pilot study, the current design is advanced.

## 8. DATA HANDLING

## 8.1 Web Data Entry

Clinical data and research questionnaires will be captured through REDCap, an encrypted, password protected database developed for the purpose of clinical research. REDCap has been embraced by the CTSA program of the NIH. Data entry is performed via REDCap by trained study coordinators at each clinical site. An electronic copy of the REDCap submission is available at the end of the entry session and serves as the source document kept at the clinical site. Lung function data are entered by the clinical coordinators, but source documents are saved electronically according to Good Clinical Practice.

## 8.2 Data Sharing

All data collected in this study will be published in a peer reviewed medical journal to support access of imatinib mesylate to patients if it is effective in LAM. This study also allows for the collection of plasma, blood mononuclear cell RNA and DNA and urine from patients on sirolimus and on imatinib mesylate that will allow a large community of researchers to study these biosamples for differences in biologic activity of these two medications. When distributing these unique resources, the PI would include pertinent information on the nature, quality, or characterization of the materials. In addition, the PI will submit unique biological information, if samples are measured, to the appropriate data banks so that they can be made available to the broad scientific community.

At the end of the study the PI will share data with any interested party via a data-sharing agreement to impose a minimum of limitations on users. First publication rights and acknowledgement of original investigators in future secondary publications would be necessary for data access. Privacy and confidentiality standards will ensure data security at the recipient site, and prohibitions for manipulating data for the purposes of identifying subjects will be put in place.

## 8.2.1 Biobank

Biosamples will remain at MUSC, Columbia University, or the University of Cincinnati during the study until study parameters are complete. With informed consent, samples that are left after study completion will be kept in biorepositories at the respective institutions and will be available for sharing with qualified researchers. The informed consent form explains that samples may be transferred to qualified researchers with coded participant information, but without use of protected health information (PHI). Biosamples will not be sent to researchers with attached PHI.

Biosamples will be available at the end of study for the larger number of LAM researchers to access the biosamples through a data and biosample sharing agreement with MUSC and/or Columbia University. Although the number of biosamples will be small, the ability to study active disease pathways between two medications used in humans is an attractive resource that would be advertised to the researcher community through the LAM Foundation and CDMRP resource listings. Shipping and laboratory costs would be paid by the requesting parties.

The biosamples will be collected under an informed consent that asks optional permission to re-contact the participant in order to link biosamples with future clinical events and introduce future LAM-related research opportunities. With effort ongoing to develop a LAM Registry through the University of Cincinnati, future research opportunities include the possibility of sample transfer if a larger biobank specific to LAM develops. If the LAM Foundation establishes such a biorepository, participants in this study who have given permission for biobanking of sample(s) and for recontact would be contacted prior to transfer of any biosample and consented with the new LAM biorepository consent form from the new site.

## 9. STUDY MONITORING

## 9.1 Data Fidelity and Quality Control

The clinical and biospecimen output data linked to a study ID will be archived and stored in the secure study database for a period of no less than 5 years after conclusion of the study. Data is password protected and secured by physical and firewall protected means.

## 9.2 Biospecimen Quality Control

Samples for study analysis related to clinical safety and efficacy are obtained, transported and processed through protocols of clinical laboratories at each institution. Samples for storage and biobank use, as expressly indicated in the participant's informed consent, are kept in dedicated repositories with all sample use logged. Quality control to define stability of all freezer temperatures and sample integrity is performed regularly.

## 9.3 Data Safety Monitoring Board

An independent Data Safety Monitoring Board (DSMB) composed of 3 individuals (2 pulmonary specialists and one regulatory/statistical clinical trial specialist) will be established to provide independent benefit/risk oversight during the conduct of the study. The DSMB will: 1) Review the protocol and consent form prior to study initiation, 2) Evaluate Serious Adverse Events on an "as needed" basis and all adverse events on a quarterly basis, 3) Recommend discontinuation of the study in the event of the occurrence of Serious or Unexpected Adverse Events that are determined by the DSMB to pose a significant safety concern. The Chairperson of the DSMB will notify the HRPO and [name] who will in turn notify the FDA or other regulatory bodies of adverse safety outcome information sufficient to stop the study. This information will also be reported as part of required regulatory progress update reports.

